12.2.5. Assessment of Severity

Grade each AE for severity and note in the description of the AE. Determine the severity category of mild, moderate, or severe, as defined below, and enter the information on the AE page of the CRF.

- Mild—causing no limitation of usual activities
- Moderate—causing some limitation of usual activities
- Severe—causing inability to carry out usual activities

12.3. Serious Adverse Events

12.3.1. Definition of Serious Adverse Event

A serious adverse event (SAE) is any AE occurring at any dose that results in any of the following outcomes, regardless of relationship to the study medication:

- Death
- A life-threatening adverse drug experience
- Inpatient hospitalization or prolongation of existing hospitalization
- A persistent or significant disability/incapacity
- A congenital anomaly/birth defect

- Important medical events that may not result in death, be life-threatening, or require hospitalization may be considered an SAE when, based upon appropriate medical judgment, they may jeopardize the subject and may require medical or surgical intervention to prevent one of the outcomes listed in this definition.

12.3.2. Reporting Serious Adverse Events

Any SAE that occurs from the time the subject signs an ICF until 30 days after taking the final dose of study medication must be reported by the investigative staff to the Sponsor or the Sponsor's representative within 24 hours of knowledge of the event (see [Study Contact Information](#)).

An SAE form must be completed and sent to the Sponsor and/or the Sponsor's representative. All SAEs must also be recorded on the AE page of the CRF. Additionally, all SAEs must be reported to the institutional review board (IRB) per the IRB's requirements.

Those SAEs that are considered both serious and unexpected and related to the study drug are subject to expedited reporting. An "unexpected AE" is any AE where the nature or severity is not consistent with the current investigator brochure (IB) or if an IB is not required or available, the specificity or severity is not consistent with the provided risk information.

Unexpected fatal or life-threatening SAEs related to the study drug must be reported by the Sponsor to the appropriate regulatory authority in an expedited manner (ie, first report within 7 days of first knowledge by the Sponsor). The Sponsor will provide a final written report to that authority within 15 days of initial receipt of information on the event. The Sponsor or the Sponsor's representative will also inform all participating Investigators of the SAE.

Unexpected SAEs that are not fatal or life-threatening must be reported by the Sponsor to the appropriate regulatory authority as soon as possible but no later than 15 calendar days after first knowledge of the SAE by the Sponsor. The Sponsor or the Sponsor's representative also informs all participating Investigators of the SAE.

Subjects withdrawn from the study due to any SAE will be followed until the SAE is resolved or medically stable. Record all SAEs, regardless of severity and whether or not related to the study medication, on the appropriate page of the CRF.

The Investigator must determine whether the seriousness of the event warrants removal of the subject from the study. He/she should, in any case, institute appropriate diagnostic and therapeutic measures and keep the subject under observation for as long as is medically indicated, or refer the subject to appropriate health professionals.

12.4. Pregnancy

Any pregnancy that occurs from the time the subject signs an ICF until 30 days after taking the final dose of study medication must be reported within 24 hours to the Sponsor or the Sponsor's representative and the subject should be terminated from the study. All pregnancies will be followed through to delivery of the infant. If the subject experiences a termination of the pregnancy, it should be reported as defined in [Section 12.3.2](#).

12.5. Other Safety Parameters and Related Information

Additional safety parameters (laboratory tests, 12-lead ECGs, physical examinations, and vital signs), the C-SSRS, the GCSI, and concomitant medications are collected as shown in the Schedule of Assessments in [Section 8](#) and evaluated over the course of the study. Clinical laboratory assessments are listed in [Appendix C](#).

13. STATISTICS

13.1. Study Design and Sample Size Estimation

This study is an open-label study in PD subjects. All subjects who successfully complete IPX203-B16-02 are eligible to enroll in this study; it is estimated that approximately 300 subjects will be enrolled.

13.2. Demographics and Baseline Characteristics

Prestudy subject demographics and baseline characteristics will be summarized to describe the subject population.

13.3. Analysis of Efficacy/Clinical Utility Data

The MDS-UPDRS Parts I to IV, PGI-S, CGI-S, PDQ-39, PDSS-2, PAS, NMSS, ZBI-12, and EMSQ will be assessed at every visit. The TSA will be assessed at every visit postbaseline. These data, along with the IPX203 dose and frequency information, will help characterize the clinical utility of IPX203. These measures will be analyzed as follows:

MDS-UPDRS – The Total MDS-UPDRS and each of its components (Parts I through IV), and Parts II and III combined, as well as the changes from Baseline in these scores, will be summarized across each of the time points in the trial (Baseline/Visit 1, Month 3, Month 6, Month 9) to allow for clinical assessment of the continuing effect of IPX203 and of switching to IPX203 for those who were randomized to IR CD-LD. For example, subjects randomized to IR CD-LD in Study IPX203-B16-02, will be examined for clinical improvement when switching to and following on IPX203 treatment. Subjects randomized to IPX203 in Study IPX203-B16-02 will be examined for maintaining clinical effect on IPX203.

PGI-S – Subjects' global impression of the severity of their PD and its treatment with IPX203 will be summarized at Months 3, 6, and 9 to assess the overall impact of IPX203 treatment over time. The mean changes from Baseline/Visit 1 in PGI-S as well as the frequencies and percentages of each component of the PGI-S will be summarized over time. The proportion of subjects with a PGI-S ≥ 4 and PGI-S ≥ 5 will also be summarized over time.

CGI-S – Clinicians' global impression of the severity of the subject's PD and its treatment with IPX203 will be summarized at Months 3, 6, and 9 to assess the overall impact of IPX203 treatment over time. The mean changes from Baseline/Visit 1 in CGI-S as well as the frequencies and percentages of each component of the CGI-S will be summarized over time. The proportion of subjects with a CGI-S ≥ 4 and CGI-S ≥ 5 will also be summarized over time.

PDQ-39 – The PDQ-39 and its domains will be assessed in the same manner as the MDS-UPDRS.

PAS – The PAS and its subscales (persistent anxiety, episodic anxiety, and avoidance behavior) will be assessed in the same manner as the MDS-UPDRS.

NMSS – The NMSS and individual domain will be assessed in the same manner as the MDS-UPDRS.

PDSS-2 – The PDSS-2 (the total score and each component) will be summarized across all visits.

TSA – The TSA will be summarized across all visits.

ZBI-12 – The ZBI-12 will be summarized across all visits.

EMSQ – The proportions of subjects with each of the early morning symptoms, the severity of each symptom, and whether the symptom improves after Parkinson's medication will be summarized across all visits. The change from baseline in total severity score will also be summarized across all visits.

13.4. Analysis of Dosing Data

Frequency of daily dosing and total daily dose of IPX203 at each visit after the baseline visit (Visit 1) will be summarized and compared against the baseline/Visit 1 daily dosing frequency. Percentages of subjects who require up-titration and down-titration, as well as the number of titration steps, will be summarized.

13.5. Population Analysis and Handling of Dropouts

Assessments will be made on available data with no adjustments for dropouts.

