8.5. Early Termination

Subjects who withdraw early should complete Study Exit procedures described in [Section 8.4](#).

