11. ASSESSMENT OF EFFICACY

To allow for assessment of the sustainability of the clinical effect of IPX203 over the 9-month study duration, the following clinical utility measures will be assessed at every visit: PGI-S, CGI-S, TSA, PDSS-2, PDQ-39, PAS, NMSS, MDS-UPDRS Parts I to IV, ZBI-12 and EMSQ.

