2.2.2 Intent-to-Treat Analysis Set

The Intent-to-treat Analysis Set (ITT) will include all subjects who were treated with the open-label study drug in the study and have at least one post-baseline clinical utility assessment.

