2.4 Early Termination Visits

Early termination visits and Visits 4 are collected in the study database as a single Visit/ET visit. For the purposes of by-visit summaries two separate visits will be presented:

- Visit 4 (identified as Visit 4/ET from the study database for subjects who completed the study)
- Visit 4/ET (i.e. all visits collected as Visit 4/ET in the study database)

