4 CLINICAL UTILITY ANALYSES

4.1 Imputation of missing data

Generally, missing data will not be imputed and data will be summarized as observed. Imputations will be performed for partially missing MDS-UPDRS responses as detailed in the following section.

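### Month 9 sustainability rests on as-observed summaries with no dropout adjustment; it may overstate maintenance, and the Visit 4/ET row only partly offsets this

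*Protocol*

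**What the plan says.** Protocol section 11 gives the purpose of the repeated clinical utility assessments: "To allow for assessment of the sustainability of the clinical effect of IPX203 over the 9-month study duration". Protocol 13.5 then sets the handling of withdrawals: "Assessments will be made on available data with no adjustments for dropouts". SAP 4.1 agrees: "Generally, missing data will not be imputed and data will be summarized as observed". Its one exception, in SAP 4.1.1, fills in a limited number of unanswered MDS-UPDRS items. It does not deal with missed visits.

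SAP 2.4 splits the last assessment into two rows. The first is "Visit 4 (identified as Visit 4/ET from the study database for subjects who completed the study"). The second is "Visit 4/ET (i.e. all visits collected as Visit 4/ET in the study database"). Exit data are requested from leavers: "Subjects who withdraw early should complete Study Exit procedures described in" Protocol section 8.4.

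The utility tables use the ITT set, which is limited to treated subjects who "have at least one post-baseline clinical utility assessment". SAP 3.1 tabulates discontinuations by primary reason and prior treatment group, with a separate line for COVID-19. The SAP contains no repeated-measures model, no sensitivity analysis for missed visits, and no utility table split by completion status.

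**The concern.** Protocol 7.3 lists lack of efficacy and adverse event among the reasons for withdrawal, and leavers are not replaced. Protocol 9.2.2 also requires discontinuation for prohibited medication, so a subject who turns to Rytary or Duopa leaves the study. If those who leave are doing worse, the remaining group improves at each visit by selection alone. A level or improving by-visit curve could then reflect either a maintained effect or selective exit, and no planned table separates the two.

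Two features of the SAP add to this.
- **Exit values.** A subject who leaves around Month 4 has the exit assessment stored as Visit 4/ET. Data are analysed by nominal visit, and the 14-day substitution rule in SAP 2.3 covers only unscheduled visits. The exit value therefore appears only in the pooled final row, beside true Month 9 values.
- **Missing data among those who stay.** SAP section 6 excludes remote Part III and CGI-S ratings. SAP 4.1.1 drops the whole MDS-UPDRS for an assessment when a part has too many missing items. The subjects contributing to the total and to Parts II+III can therefore differ by visit.

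At stake is how far the sustainability statement can be read as applying to the subjects who entered the extension.

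**Working it through.** The documents give no dropout rate, SD, effect size or sample-size formula, so there is no stated figure to reproduce. The calculation below is an illustration.

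**Inputs**
- N = 300, from Protocol 13.1: "it is estimated that approximately 300 subjects will be enrolled". This is an expected roll-over count.
- d = share of subjects who drop out. Assumed, 5% to 30%.
- g = how much worse the leavers' Month 9 change would be than the completers', in SDs of change. Assumed, -0.25 to 1.0.
- a = share of leavers with an exit assessment. Assumed, 80% in the table.
- c = share of the gap already visible at exit. Assumed, 50% or 100%.

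**Completer row (Visit 4).** Set the completers' mean change to 0, with worse scored as positive. The mean for all starters is (1 - d) × 0 + d × g = d × g, so the completer row is too favourable by d × g. The standard error of the completer mean is 1/√(300 × (1 - d)).

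**Pooled row (Visit 4/ET).** Its mean is d × a × c × g / ((1 - d) + d × a). The remaining bias is d × g minus that quantity.

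**Worked case: d = 0.20, g = 0.5**
- Completer bias: 0.20 × 0.5 = 0.10 SD.
- Standard error: 1/√240 = 0.0645 SD, so the bias is 0.10/0.0645 = 1.55 standard errors.
- Coverage: a nominal 95% interval around the completer mean would cover the all-starter mean with probability Φ(1.96 - 1.55) - Φ(-1.96 - 1.55), about 66%. The SAP plans no such interval; this is only a yardstick.
- Visit 4/ET with a = 0.8, c = 0.5: 0.10 - 0.04/0.96 = 0.058 SD.
- Visit 4/ET with a = 0.8, c = 1.0: 0.10 - 0.08/0.96 = 0.017 SD.

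**Across dropout shares, with g = 0.5 and a = 80%**

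| d | Completers | Visit 4 bias (SD) | SE (SD) | Bias/SE | Visit 4/ET bias, c = 50% | Visit 4/ET bias, c = 100% |
|---|---|---|---|---|---|---|
| 10% | 270 | 0.05 | 0.061 | 0.82 | 0.030 | 0.009 |
| 20% | 240 | 0.10 | 0.065 | 1.55 | 0.058 | 0.017 |
| 30% | 210 | 0.15 | 0.069 | 2.17 | 0.086 | 0.022 |

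**Sensitivity to g.** At d = 20%, the completer-row bias is 0.20 SD for g = 1.0, zero for g = 0, and -0.05 SD for g = -0.25, where the sign reverses. Over d from 5% to 30% and g from 0 to 1.0, it runs from 0 to 0.30 SD.

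The bias in SD units does not depend on N. Only the comparison with the standard error does, and that ratio would be smaller within a single prior-treatment group.

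**The case against.** A reader might infer that the Month 9 result is biased toward a maintained effect. The documents do not support that as a fact. They report no dropout rate and nothing about leavers' outcomes. Of the nine withdrawal reasons in Protocol 7.3, only lack of efficacy and adverse event clearly imply a worse course. Sponsor termination, protocol deviation and COVID-related exit need not. The bias is zero if leavers resemble stayers and reverses if they do better.

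A reader might also infer that Month 9 describes only those who stayed. It does not: the Visit 4/ET row brings in exit assessments, and the protocol asks for them. Under the assumptions above, that row removes about 40% of the bias or more. It still mixes assessment times and misses leavers with no exit visit.

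A third temptation is to express the bias in points and set it against the 4-unit Part III change in Protocol section 4. That figure was a threshold for measuring duration of effect in an earlier crossover study. It is not a margin for 9-month sustainability and does not carry over to the MDS-UPDRS total, Parts II+III or PGI-S.

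It is also fair to say that the analyses are descriptive. There is no hypothesis test, so no error rate or power is affected. Attrition is disclosed by reason, and subject and missing counts are shown. Change from baseline is within subject, so different baseline levels alone do not bias it, although raw visit means remain exposed. Dose changes and added PD treatments are permitted without a control arm, which already limits what a flat curve can mean.

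These points limit the claim and its weight. They do not supply an analysis that distinguishes a maintained effect from selective exit.

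**Conclusion.** The gap is real but moderate. The sustainability statement will rest on as-observed summaries. One final row is completers only, the other blends Month 9 with earlier exits, and the SAP does not say which is relied on. The Month 9 summary may overstate maintenance; whether it does, and by how much, cannot be settled from the documents. Under the assumed case of 20% dropout and a 0.5 SD worse change in leavers, the overstatement is 0.10 SD in the Visit 4 row. It is about 0.06 SD in the Visit 4/ET row if 80% of leavers have an exit visit showing half the gap. No inferential quantity in the plan is invalidated. The improvement is worth making because it is cheap, uses data already collected, and bears directly on how a flat curve should be read.

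**What to change.** Before the SAP is finalised:

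1. Keep the as-observed tables, and state which row (Visit 4 or Visit 4/ET) supports the sustainability statement.
2. Add by-visit change-from-baseline tables split by completers and discontinuers. These show directly whether leavers were doing worse before they left.
3. Add a supportive mixed model for repeated measures on all observed post-baseline visits, for MDS-UPDRS total, Parts II+III and PGI-S. Assign each exit value to the next scheduled post-baseline visit the subject has not yet had. It should never go to Baseline and never overwrite a recorded visit. A nearest-visit rule would not do: it could send a very early exit to Baseline, or a Month 4 exit to a Visit 2 that already holds a value.
4. Add a delta-adjusted sensitivity analysis for dropouts due to lack of efficacy or adverse event, over a range prespecified for each endpoint. The scales differ too much for a common delta: PGI-S runs from 1 to 7, so its change cannot exceed 6 points.

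The cost is SAP text and modest programming, with no new data. The downside is a supportive estimate that relies on missing-at-random, which is why item 4 accompanies it. Treated subjects with no post-baseline utility assessment stay outside the ITT set. Their number can be read from the Safety and ITT counts already planned in SAP 3.1 and should be mentioned beside the result.

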13.6. Analysis of Safety

The safety analysis will include all subjects who received at least one dose of study medication. Adverse events, supine and standing orthostatic vital signs, concomitant medications, electrocardiograms (ECGs), clinical laboratory tests, physical examinations, and the Columbia-Suicide Severity Rating Scale (C-SSRS) will be evaluated throughout the course of the study.

Adverse events will be collected and summarized both for the time in the open-label extension trial and the time of overall IPX203 exposure. For summary and reporting purposes, “unlikely related,” “possibly related,” and “related” will be combined and will be counted as “related.”

Vital signs and ECGs will be summarized across the entire IPX203 exposure including information from the open-label extension and the prior IPX203-B16-02 study into which the subjects were enrolled.

14. ADMINISTRATIVE PROCEDURES

14.1. Guidelines for Good Clinical Practice

This study will be conducted in accordance with principles of Good Clinical Practice (GCP) as promulgated by the ICH. Good Clinical Practice is an international ethical and scientific quality standard for designing, conducting, recording, and reporting trials that involve the participation of human subjects. Compliance with this standard provides public assurance that the rights, safety, and well-being of human subjects are protected under current ethical principles, and that the clinical trial data are credible. Current GCP standards may be found in ICH Guidance E6 (Good Clinical Practice: Consolidated Guidance). This guidance describes the principles of GCP and the obligations of the institutional review board (IRB), the Investigator and the Sponsor in conducting this study in accordance with those principles.

14.2. Institutional Review Board Approval

The review of this protocol by an IRB and the performance of all aspects of the study, including the methods used for obtaining informed consent, must be in accordance with principles enunciated in the ICH and GCP Guidelines and by the appropriate regulatory authorities.

The Investigator is responsible for preparing documents for submission to the relevant IRB and obtaining written approval for this study. Institutional Review Board approval must be obtained prior to the initiation of the study. The Investigator's continued participation in the study is contingent on renewing approval with the IRB at least annually.

14.3. Informed Consent

Site personnel should prepare an Informed Consent Form (ICF) incorporating the necessary elements of consent. The ICF is to be approved by Impax prior to submission to the IRB. The Investigator or his/her staff must explain the nature of the investigation and the risks involved to each subject prior to screening, and obtain a signed ICF. The subject should also be informed that he/she is free to voluntarily withdraw from the study at any time.

14.4. Study Monitoring

Impax representatives or designees will conduct site visits to the investigational facilities for the purpose of monitoring the study. The Investigator agrees to allow the monitor to inspect the drug storage area, study drug stocks, drug accountability records, subject charts and study source documents, and other records relevant to study conduct. The Investigator must permit access to such records if a regulatory or compliance audit is required.

14.5. Protocol Amendments

All amendments to the protocol must be documented in writing, reviewed and approved by the Sponsor and Investigator, and submitted to the IRB for approval prior to implementation. If the protocol amendment substantially alters the study design or potential risk to the subject, a new

written ICF for continued participation in the study must be obtained from each subject affected by the change.

14.6. Termination of Study

The Sponsor has the right to terminate this study and remove all study material from the site at any time for medical or administrative reasons. In this event, the Sponsor will endeavor to give adequate notice to allow safe withdrawal of subjects from the study.

14.7. Case Report Forms

Site personnel should collect and record data for the study as source documents, and transfer the data into the CRF.

The Investigator must ensure that complete data for the clinical study are collected and accurately documented in the appropriate sections of the CRF and adequately supported by the appropriate source documentation. In addition, it is the Investigator's responsibility to provide signatures where requested indicating concurrence with data in the CRF.

14.8. Investigator's Final Conduct Report

At the completion of the study, the Investigator must provide Impax a copy of the final conduct report that was submitted to their IRB, including a review of AEs.

14.9. Records Retention

International Conference on Harmonization, GCP, and US FDA guidelines require that essential documents be retained until at least 2 years after the last approval of a marketing application and until there are no pending or contemplated marketing applications, or at least 2 years have elapsed since the formal discontinuation of clinical development of the investigational product.

However, the essential documents should be retained for a longer period if required by the applicable regulatory requirements or by an agreement with the Sponsor. Records should never be destroyed without written approval from the Sponsor.

If an Investigator leaves the institution, he/she must transfer responsibilities for record retention to another individual willing to accept them. The Investigator must notify the Sponsor in writing of the transfer of study documents before the transfer of the study documents.

